4.3.2.2. Withdrawal of Consent to Process the Patient's Personal Data

Where allowed by local law, the patient may decide to withdraw consent to collect, store, and use biological samples and, as applicable, other personal data, informing the study doctor at any time in writing or in any other form that may be locally required. The Sponsor will continue to keep and use the patient's study information (including any data resulting from the analysis of the patient's biological samples until the time of withdrawal) according to applicable law. The process for the storage and, as applicable, further use of remaining samples will be followed per local requirements.

4.3.2.3. Investigator or Sponsor Stops Participation of a Patient in the Study

The Investigator or Sponsor may stop the participation of a patient in the study at any time if this is considered to be in the patient's best interest. However, study integrity and interpretation are best maintained if all enrolled patients continue study assessments and follow-up through Month 6 even if study drug is discontinued.

Termination of the clinical study and site closure are described in Section 8.1.6.

4.3.2.4. Recording Reason for Stopping a Patient's Study Participation

The primary reason that a patient's study participation is stopped must be recorded in the appropriate section of the electronic case report form (eCRF) and all efforts will be made to complete and report the observations as thoroughly as possible. If a patient's study participation is stopped due to an AE, including SAEs, the event should be followed as described in Section 6.5.6.

4.3.3. Lost to Follow-Up

A patient will be considered lost to follow-up if the patient repeatedly fails to return for scheduled visits and is unable to be contacted by the clinical study center. The following actions must be taken if a patient misses a required study visit:

- The site must attempt to contact the patient or legal guardian and reschedule the missed visit as soon as possible and counsel the patient or legal guardian on the importance of maintaining the assigned visit schedule and ascertain if the patient or legal guardian wishes [for the patient] to continue in the study, and/or should continue in the study.

- Before a patient is deemed lost to follow up, the Investigator or designee must make every effort to regain contact with the patient or legal guardian by 3 telephone calls and, if necessary, a certified letter to the patient's last known mailing address or local equivalent methods. These contact attempts should be documented in the patient's medical record.
- Should the patient or legal guardian continue to be unreachable, the patient will be considered to have stopped participation in the study.
- For patients who are lost to follow-up, the Investigator or designee should search publicly available records (where permitted and allowed by local law) to ascertain survival status. This ensures that the outcome of the study is as comprehensive as possible.

4.3.4. Replacement of Study Patients

Patients who discontinue the study drug or stop participation in the study prior to Month 6 may be replaced at the Sponsor's discretion. Patients who crossover from Cohort A to Cohort B due to progressing to dialysis prior to Month 6 also may be replaced at the Sponsor's discretion. Patients who discontinue the study drug or stop participation in the study after Month 6 will not be replaced.

5. TREATMENTS AND OTHER REQUIREMENTS

5.1. Treatments Administered

Study drug supplied for this study must not be used for any purpose other than the present study and must not be administered to any person not enrolled in the study. Study drug that has been dispensed and returned unused must not be re-dispensed.

5.2. Study Drug

Detailed information describing the preparation, administration, and storage of lumasiran is provided in the Pharmacy Manual.

5.2.1. Description

Lumasiran will be supplied as a sterile solution in water for SC injection. See the Pharmacy Manual for further details of solution concentration and fill volume.

5.2.2. Dose and Administration

Patients will be administered lumasiran as an SC injection at the dose and regimen based on their weight category as described in Table 10. Liver function test clinical laboratory assessments (see Table 13) from the Week 2 visit must be reviewed prior to administration of the Month 1 dose, as specified in the Schedules of Assessments (Table 1). The LFT criteria for withholding, monitoring, or stopping dosing is described in Section 5.2.3.1. Patients will receive 3 loading doses, once monthly (at Day 1, Month 1, and Month 2) at a dose based on body weight category. At Month 3 and beyond, patients will receive lumasiran either monthly (patients weighing

<10 kg) or every 3 months (patients weighing \geq 10 kg) at the maintenance dose. Study drug administration must be at least 21 days apart. In patients on dialysis therapy, study drug should be administered as soon as feasible following the end of dialysis, ie, no later than 120 minutes post-dialysis.

Study drug injections will be administered under the supervision of the Investigator. The site of injection may be the abdomen, the upper arms or thighs. If a local reaction around the injection site occurs, photographs may be obtained. Detailed instructions for study drug administration are found in the Pharmacy Manual.

Dosing will be permitted at a location other than the study center (for example, the patient's home) by a healthcare professional with the oversight of the Investigator at all time points, provided the patient has tolerated at least 1 dose of lumasiran administered in the clinic. However, continued study drug administration at the study center should be considered for patients who have ongoing study drug-related AEs, worsening injection site reactions with repeat dosing, or for anyone in the opinion of the Investigator who would benefit from clinical observation following dosing.

If the patient is unable to come to the study site, and a visit by a healthcare professional is not possible due to circumstances related to the COVID-19 pandemic, lumasiran may be administered by the patient or patient's caregiver under the oversight of the Investigator, and following consultation with the Medical Monitor, as allowed by applicable country and local regulations. In such cases, the patient/caregiver must receive appropriate training on lumasiran administration prior to dosing. This measure is intended to remain in effect only during periods of time when the COVID-19 pandemic impedes the ability of patients to travel to the study site and healthcare professionals to go to patients' homes for dosing.

In addition, assessments specific to measures of systemic oxalosis (eg, observing and photographing skin lesions during physical examinations) must be performed at the study center for the duration of the study, as specified in the Schedules of Assessments (Table 1, Table 2 Table 3, Table 4).

Table 10: Weight-based Dosing Regimen

Weight	Loading Dose (Day 1, Month 1, Month 2)	Maintenance Dose (Month 3 and Beyond)
<10 kg	6.0 mg/kg monthly for 3 months	3.0 mg/kg monthly
\geq 10 to <20 kg	6.0 mg/kg monthly for 3 months	6.0 mg/kg every 3 months
\geq 20 kg	3.0 mg/kg monthly for 3 months	3.0 mg/kg every 3 months

For patients <6 years of age, the dose will be based on a weight obtained within 7 days prior to dosing. In patients \geq 6 years of age, body weight collected within 3 months prior to the study drug dose or the predose weight collected on the study visit day or dosing day will be used for dose calculations.

During periods of time when the COVID-19 pandemic impedes the ability of patients to travel to the study site and healthcare professionals to go to patients' homes, the dose will be based on weight obtained within 6 weeks prior to dosing for patients who are <10 kg and within 4 months for patients who weigh \geq 10 kg. For Cohort B patients, if a post dialysis weight taken at the study

center is not available within the specified timepoints, post dialysis weight taken at the dialysis center may be used.

Patients with weight increases crossing the threshold for the next weight-based dosing category (<10 kg to \geq 10 kg or <20 kg to \geq 20 kg) will follow the new dosing regimen for the remainder of the study or until the next dosing category threshold is reached (ie, patients will not switch back to the lower-weight dosing schedule if their body weight subsequently decreases).

Patients in maintenance dosing who transition from <10 kg to \geq 10 kg will continue to receive monthly doses at 3.0 mg/kg until the next visit that coincides with Table 4, whereby they will follow every-3-months dosing as per Table 4 until the end of the study.

If a patient does not receive a dose of lumasiran within the specified dosing window, the Investigator should contact the Medical Monitor. After such consultation, the dose may be administered or considered missed and not administered.

If a patient misses multiple consecutive doses, the Investigator, in consultation with the Medical Monitor, will discuss whether the patient will be able to continue the study (see Section 4.3).

Additional details can be found in the Pharmacy Manual. In addition, instructions and procedures related to the administration of lumasiran by a patient or caregiver will be provided in the Patient/Caregiver Storage and Administration Instructions.

5.2.3. Dose Modifications

Dose modifications are not permitted.

If a study drug-related AE occurs in a patient that the Investigator judges as presenting a potential risk to the patient for further dosing, the study drug dose may be held at the discretion of the Investigator and the Medical Monitor should be contacted.

5.2.3.1. Liver Function Test Criteria for Withholding, Monitoring and Stopping Lumasiran Dosing

1. Liver function test (LFT) results (see Table 13) are to be obtained within 7 days prior to dosing and results are to be reviewed prior to each dose of lumasiran. During periods of time when the COVID-19 pandemic impedes the ability of patients to travel to the study site and healthcare professionals to go to patients' homes and LFT assessments are not feasible within 7 days prior to the dose, LFT test results up to 6 weeks prior to the planned monthly dose or up to 4 months prior to the planned quarterly dose may be reviewed to determine whether the dose can be administered. Consult the Laboratory Manual for the blood draw priority list based on patient weight. Central laboratory results are preferable. If not available, local laboratory results may be used; however, if a local assessment is drawn, a serum chemistry sample must also be drawn for analysis at the central laboratory.
2. For any ALT or AST elevation $>3\times$ ULN, central laboratory results should be used to guide subsequent monitoring as detailed in Table 11.
3. For any ALT or AST elevation $>3\times$ ULN:

- a. If local laboratory results are obtained, confirm using central laboratory, as soon as possible, ideally within 2 to 3 days, but no later than 7 days.
- b. If an alternative cause is found, provide appropriate care.
- c. If an alternative cause is not found, perform assessments per Table 11 and Table 14.

4. For any ALT or AST elevation $>3 \times$ ULN without alternative cause that is accompanied by clinical symptoms consistent with liver injury (eg, nausea, right upper quadrant abdominal pain, jaundice) or elevated bilirubin to $\geq 2 \times$ ULN or international normalized ratio (INR) ≥ 1.5 , permanently discontinue dosing.
5. For confirmed ALT or AST elevations $>3 \times$ ULN without alternative cause and not accompanied by symptoms or elevated bilirubin $\geq 2 \times$ ULN or INR ≥ 1.5 , see Table 11.

Table 11: Monitoring and Dosing Rules for Asymptomatic Patients with Confirmed Isolated Elevations of ALT and/or AST $>3 \times$ ULN, with No Alternative Cause Identified

Transaminase Level	Action
$>3 \times$ to $5 \times$ ULN	
 • May continue dosing • Evaluate the initial elevation in LFT per the following assessments: 
 • Table 14 (all assessments to be performed; see Section 6.5.5.4 for guidance on maximal pediatric blood volumes) • Hematology, serum chemistry, and LFT per Table 13 • Coagulation (prothrombin time, partial thromboplastin time, international normalized ratio) • Monitor at least every two weeks: LFT per Table 13 • If elevation persists for ≥ 2 months, must discuss with the Medical Monitor before continuing dosing
$>5 \times$ to $8 \times$ ULN	
 • Hold lumasiran dosing until recovery to $\leq 1.5 \times$ ULN or baseline; may resume dosing after discussion with the Medical Monitor • Evaluate the initial elevation in LFT per the following assessments: 
 • Table 14 (all assessments to be performed once) • Hematology, serum chemistry, and LFT per Table 13 • Coagulation (prothrombin time, partial thromboplastin time, international normalized ratio) • Monitor at least weekly: LFT per Table 13 until ALT and/or AST is declining on 2 consecutive draws, then may decrease monitoring to biweekly • If ALT or AST rises to $>5 \times$ ULN following resumption of dosing, permanently discontinue dosing
$>8 \times$ ULN	Permanently discontinue dosing after confirmation by the central laboratory of the transaminase value

Abbreviations: ALT=alanine aminotransferase; AST=aspartate aminotransferase; LFT=liver function tests; ULN=upper limit of normal.

Notes: In addition to these criteria, other assessments or evaluations may be performed per Investigator discretion, as appropriate. See the Study Manual for sample priority list.

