of lumasiran have at least 1 postdose blood sample for PK parameters and have evaluable PK data.

The primary population used to evaluate efficacy will be the Efficacy Analysis Set and safety will be the Safety Analysis Set. The PK Analysis Sets will be used to conduct PK analyses.

The primary analysis is percent change from baseline in plasma oxalate (Cohort A) / pre-dialysis plasma oxalate (Cohort B) summarized through Month 6 by cohorts. Secondary endpoints will be analyzed and reported with by-patient listings and by-patient figures of actual values, change from baseline and percent change (where change in percent is applicable) at each visit (scheduled and unscheduled visits). Tabular summaries using descriptive statistics (mean, standard error, median, min, max) will be reported. Long-term treatment effect of lumasiran will be summarized descriptively for the long-term extension period. Safety data will be summarized descriptively and presented in by-patient listings.

Table 1: Schedule of Assessments –Primary Analysis Period (Screening through Month 6): All Patients
After Month 6, patients with weight <10 kg follow Table 2. Patients with weight ≥10 kg follow Table 4.

Study Period	Study Visit	Screening	6-Month Primary Analysis Period							
			D1	Wk 2	M1	M2	M3	M4	M5	M6
Study Day (±Visit Window)*	Notes	-120 to -1	1 (±3)	15 (±4)	29 (±4)	57 (±4)	85 (±4)	113 (±4)	141 (±4)	169 (±7)
Informed consent	Section 8.1.1	X								
Demographics	Section 6.1	X								
Medical history	Section 6.1	X	X							
Inclusion/exclusion criteria	Section 4.	X								
Full PE	Section 6.5.3	X								X
Abbreviated PE	Section 6.5.3		X	X	X	X	X	X	X	
Height/length	Section 6.5.2	X	X		X (<6 y)	X (<6 y)	X	X (<6 y)	X (<6 y)	X
Body weight	Section 6.5.2	X	X		X	X	X	X	X	X
Vital signs	Section 6.5.1	X	X	X	X	X	X	X	X	X
12-lead ECG	Triuplicate. Repeat if done ≥60 days before D1. Section 6.5.4	X					X			X
Follicle-stimulating hormone	Section 6.5.2	X								
Pregnancy test	Females of child-bearing potential. Section 6.5.5.2	X	X		X	X	X			X
DNA sample for PH1/AGXT mutation analysis	Section 6.1	X								
Exploratory DNA sample	Optional. Section 6.6		X							
Clinical laboratory assessments	Repeat serum creatinine and LFTs if collected ≥30 days before D1; Section 6.1. Section 6.5.5	X	X	X	X	X	X	X	X	X
Coagulation (PT/PTT/INR)		X								
Study drug dosing in pts <10 kg	Table 10. Dose after dialysis, if applicable.-Doses must be at least 21 days apart. Section 5.2.2		X		X	X	X	X	X	X

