Study drug dosing in pts ≥10 kg			X		X	X	X			X
Blood samples for PK analyses	Table 5 and Table 6		X							X
Urine samples for PK analyses	Table 7		X							

Table 1: Schedule of Assessments –Primary Analysis Period (Screening through Month 6): All Patients
After Month 6, patients with weight <10 kg follow Table 2. Patients with weight ≥10 kg follow Table 4.

Study Period	Study Visit	Screening	6-Month Primary Analysis Period							
			D1	Wk 2	M1	M2	M3	M4	M5	M6
Study Day (±Visit Window)*	Notes	-120 to -1	1 (±3)	15 (±4)	29 (±4)	57 (±4)	85 (±4)	113 (±4)	141 (±4)	169 (±7)
Blood samples for PD analyses (Cohort A)	Screening collections as per Figure 1, Section 6.3		X		X	X	X	X	X	X
Blood samples for PD analyses (Cohort B)	Screening collections as per Figure 1, Section 6.3		X		X	X	X	X	X	X
Blood samples for POx profile	Table 6; Pts on dialysis only. Screening collections as per Section 6.1 Figure 1.	X					X			X
24-hour urine collection (1 collection)	Table 12 and Section 6.2.2							X		
24-hour urine collection (3 collections)		X								X
Single-void urine collections (3 collections).	Collected within 7 days predose (first morning voids preferred). Section 6.2.2	X			X	X	X	X	X	X
Blood sample for pyridoxine (vitamin B6) levels	Only in pts receiving therapeutic pyridoxine, collect ≥6 hrs after dose. Section 5.3	X	X				X			X
Renal ultrasound	Section 6.3.1	X								X
Echocardiogram	Repeat if done ≥60 days before D1. Section 6.2.3.1	X								X
Radiographs	Section 6.2.3.3	X								
Ophthalmology Evaluation	Section 6.2.3.4	X								
Review/Record Dialysis Parameters	Pts on dialysis. Section 6.5.5.5	X	X				X			X
Vineland Behavior Scale	Pts <6 y at consent. Section 6.7	X								X
Quality of life questionnaires	Section 6.8	X								X
Patient/caregiver experience and impact questionnaires	Section 6.9	X								X
Healthcare resource utilization	Section 6.10				Continuous					
ADA sample	Section 6.5.5.1		X		X		X			X

Table 1: Schedule of Assessments –Primary Analysis Period (Screening through Month 6): All Patients
After Month 6, patients with weight <10 kg follow Table 2. Patients with weight ≥10 kg follow Table 4.

Study Period Study Visit	Notes	Screening -120 to -1	6-Month Primary Analysis Period							
			D1	Wk 2	M1	M2	M3	M4	M5	M6
Study Day (±Visit Window)*		-120 to -1	1 (±3)	15 (±4)	29 (±4)	57 (±4)	85 (±4)	113 (±4)	141 (±4)	169 (±7)
Blood and urine samples for exploratory analyses	Single-void urine. Samples collected predose. Section 6.6	X	X		X		X			X

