Creatinine and eGFR (Bedside Schwartz formula for children \geq 12 months to $<$ 18 years of age at consent; MDRD formula for adults \geq 18 years of age at consent)	Chloride
Pyridoxine (vitamin B6) ^a	
Liver Function Tests	
AST	ALP
ALT	Serum bilirubin (total and direct)
Urinalysis^b	
Visual inspection for appearance and color	Bilirubin
pH (dipstick)	Nitrite
Specific gravity	RBCs
Ketones	Urobilinogen
Albumin (optional)	Leukocytes
Glucose	Microscopy (if clinically indicated)
Protein	

Abbreviations: ALP=alkaline phosphatase; ALT= alanine aminotransferase; AST=aspartate aminotransferase; BUN=blood urea nitrogen; eGFR=estimated glomerular filtration rate; PH1=primary hyperoxaluria type 1; RBC=red blood cell

^a Pyridoxine (vitamin B6) is required through Month 12 and only for patients receiving vitamin B6 for the treatment of PH1. On days when a blood sample for pyridoxine will be collected, patients should be instructed not to take vitamin B6 within 6 hours prior to blood sample collection.

^b Urinalysis will not be collected in Cohort B patients who are anuric (ie, produce $<$ 100 ml of urine per day).

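### While dosing continues at unexplained ALT/AST >3× to 5× ULN, INR is required only at the first work-up, so the INR arm of the permanent-stop rule can go unchecked before every later dose

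*Protocol*

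**What the plan says.** Protocol 5.2.3.1, item 4, covers any ALT or AST elevation above 3× ULN without an alternative cause. If it comes with symptoms of liver injury, bilirubin of at least 2× ULN, or "international normalized ratio (INR) ≥ 1.5 , permanently discontinue dosing". Item 5 sends confirmed elevations with none of these three features to Table 11.

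The >3× to 5× ULN row of Table 11 permits dosing to continue. PT, PTT and INR appear there under the evaluation of the initial elevation. The continuing instruction is "Monitor at least every two weeks: LFT per Table 13". If the elevation lasts 2 months or more, the site "must discuss with the Medical Monitor before continuing dosing". A note to the table adds that "other assessments or evaluations may be performed per Investigator discretion, as appropriate".

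The liver panel in Table 13 (Protocol 6.5.5) is AST, ALT, ALP and total and direct bilirubin. It contains no INR. Item 1 of 5.2.3.1 says that liver tests "are to be obtained within 7 days prior to dosing and results are to be reviewed prior to each dose of lumasiran", with longer look-back periods allowed when COVID-19 prevents access.

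**The concern.** A patient belongs in the dosing row only while all three features in item 4 are absent. Two of the three are followed as time passes: bilirubin through the two-weekly panel, symptoms through clinical contact and adverse event review. The third, INR, is established once and then assumed. A site that follows Table 11 to the letter can give a further dose to a patient who already meets a mandatory stop criterion, because nothing required it to look.

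Protocol 1.5 names liver function test abnormality as an important potential risk and relies on the withholding and stopping rules as mitigation. A stop criterion should be measured before a dose that it would forbid. What is at stake is individual patient safety.

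**Working it through.** **1. Is INR required anywhere else after the first work-up?**

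| Place in the protocol | INR after the initial elevation |
|---|---|
| Table 1 | Coagulation marked at Screening only |
| Tables 2 to 4 | No coagulation row |
| Table 11, >3× to 5× ULN row | Listed under the initial elevation only |
| Table 13, liver panel | Not included |
| Table 14 (see also 6.5.5.3) | Not listed; panel done once |
| 6.5.5, repeat testing | Applies to a test already found abnormal, so a normal first INR triggers nothing |
| Table 11 note, 6.5.5.3 | Investigator discretion |
| 3.7 (DMC) and 5.2.3 (dose hold) | Discretionary |

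Over the first 2 months (2 × 28 = 56 days, since the protocol defines a month as 28 days) the row requires at least 56/14 = 4 liver panels after the work-up and 0 INRs. In the >5× to 8× row dosing is held until recovery, so the question does not arise there.

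**2. Doses before the Medical Monitor discussion (day 56 from detection).** Nominal dosing days from Table 1 (row "Study drug dosing in pts ≥10 kg") and Table 4: 1, 29, 57, 85, 169, 253, then every 84 days. Patients under 10 kg are dosed every 28 days.

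| Elevation found at | Days to later doses | Doses before day 56 |
|---|---|---|
| Week 2 (day 15) | 29−15 = 14; 57−15 = 42; 85−15 = 70 | 2 |
| Month 1 (day 29) | 57−29 = 28; 85−29 = 56 | 1, another on day 56 |
| Month 2 (day 57), <10 kg | 85−57 = 28; 113−57 = 56 | 1, another on day 56 |
| Month 2 (day 57), ≥10 kg | 85−57 = 28; 169−57 = 112 | 1 |
| Any later monthly visit, <10 kg | 28; 56 | 1, another on day 56 |
| Month 4 (day 113), ≥10 kg | 169−113 = 56 (windows: 162−117 = 45 to 176−109 = 67) | 0 nominally, 1 at the early end |
| Month 5 (day 141), ≥10 kg | 169−141 = 28 | 1 |
| Months 3, 6, 9 onward, ≥10 kg | 84 | 0 |

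**3. COVID-19 windows.** Table 1 widens visits after Week 2 to ±14 days, and doses must be at least 21 days apart. Suppose detection is on day 19 (Week 2 visit, +4 days), with doses on days 29, 50 and 71. The gaps are 50−29 = 21 and 71−50 = 21. Day 50 lies in the Month 2 window (57±14, days 43 to 71) and day 71 in the Month 3 window (85±14, days 71 to 99). Days from detection are 10, 31 and 52, so 3 doses fall before day 56.

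**4. After the discussion.** The row names no INR at the discussion or later. If dosing continues with the elevation above 3× ULN, each further dose (every 28 or 84 days) is in the same position. The zero in the last line of the table means no dose before the discussion; the dose at 84 days is still given with no INR required.

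**5. Blood volume of the fix.** Tube volume is not in the documents; assume 1 to 3 mL. With doses at least 21 days apart, at most 2 pre-dose draws fall in 30 days, so 2 to 6 mL. Against the 30-day, 5% column of Table 15:

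| Weight | Limit | Share used |
|---|---|---|
| 3 kg | 12 mL | 2/12 to 6/12 = 17% to 50% |
| 5 kg | 20 mL | 2/20 to 6/20 = 10% to 30% |
| 10 kg | 40 mL | 2/40 to 6/40 = 5% to 15% |

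**The case against.** The sponsor made a reasoned choice. The Amendment 1 summary (1.2) removes routine coagulation testing after Screening because no coagulation signal had been seen in any lumasiran study and because blood volume is limited in children. It lists 5.2.3.1 among the sections changed. An INR at onset followed by two-weekly transaminases, ALP and bilirubin is a coherent scheme, and other safeguards remain: the DMC may ask for more tests, the investigator may hold a dose, and the sponsor is notified of ALT or AST above 3× ULN within 24 hours (6.5.6.3).

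The harmful sequence is also specific. INR must be below 1.5 at onset and rise later, while bilirubin stays below 2× ULN, symptoms are absent and transaminases stay at or below 5× ULN. The Amendment 1 summary (1.1) reports no clinically significant liver test changes due to lumasiran in 75 PH1 patients treated for up to 22 months.

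Most of this stands as a limit on importance. It does not remove the gap. What the amendment dropped was routine testing; testing during an unexplained elevation is a different matter, and Table 11 itself still asks for INR at onset. The remaining safeguards are discretionary, depend on a test already being abnormal, or do not mention INR. The 75-patient statement supports rarity but is a judgement about clinical significance and attribution, so it cannot be read as a count of zero elevations above 3× ULN.

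**Conclusion.** The gap is real on the text. After the initial work-up the number of required INRs is 0, although INR of 1.5 or more remains a mandatory stop criterion while dosing continues. Up to 2 doses before the Medical Monitor discussion are exposed on the nominal schedule and 3 are possible under the COVID-19 windows, with no cap afterwards. These counts assume that the elevation persists in the >3× to 5× range, that no alternative cause is found, and that the site does only what is required.

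Three further readings go beyond the documents:

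- A reader might infer that exposure ends at the Medical Monitor discussion, so that 2 doses is a ceiling and patients of 10 kg or more are safe when the elevation is found at a quarterly dosing visit. The discussion requires no INR, so neither follows.
- A reader might infer that worsening liver injury would go unseen. Two-weekly bilirubin, symptoms, the >5× hold and the >8× stop all remain.
- A reader might infer an effect on the trial's results. No endpoint is affected.

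The state should be rare, though the documents do not give its frequency. This is a could-fix item, suited to the next amendment.

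**What to change.** Add one line to the >3× to 5× ULN row of Table 11: *INR is taken with the pre-dose liver draw, or with the latest two-weekly draw, and the result is reviewed before each further dose for as long as ALT or AST without alternative cause remains above 3× ULN, within the limits of Table 15.* The second option covers patients whose pre-dose draw is waived under the COVID-19 allowance.

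No extra visit or needle-stick is needed, because both draws are already required. The cost is the blood volume worked out above. It is small for most patients but could reach half of the 5% monthly limit at 3 kg, on top of the other liver work-up, so the Table 15 condition should stay in the wording. As a protocol change it also needs the approvals described in 8.1.2.

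No anticoagulant clause should be attached. Exclusion criterion 1c admits patients on oral anticoagulants with INR below 3.5, which sits awkwardly with a fixed threshold of 1.5. That conflict already arises at the initial INR and is a separate issue.
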